**Homocysteine in bariatric patients following laparoscopic roux-en-Y
gastric bypass surgery
Department of surgery
Medical university of Vienna
An exploratory study in 708 consecutive patients.**

EK1143/2013

[name]

Associate professor [name]

Department of surgery (head of department: Univ. [name], MD),
Medical University of Vienna

Translation of the original study protocol document approved by the local ethics
committee in 2014.

Table of content

1	Background	3
2	Outcome	3
3	Patients	4
4	Parameters	4
4.1	Primary outcome	4
4.2	Secondary outcomes	4
5	Methods	4
6	Statistics	5
7	Data privacy protection	5
8	Risk-benefit analysis	6
9	References	6

1 Background

Hyperhomocysteinaemia defined as serum levels above 15 $\mu\text{mol/l}$ is associated with numerous risks. There is an elevated risk in suffering from cardiovascular events (myocardial infarction, stroke, acute limb ischemia, deep veinous thrombosis) who are today's number one cause of death in the industrialized world (1). Furthermore, Homocysteine was found to be a mediator in dementia, Alzheimer's disease (2), osteoporosis induced pathological fractures (3) and diabetic retinopathia (4). The role of homocysteine in metabolic diseases is indisputable. Obesity is also associated closely with cardiovascular disease events, therefore it is necessary to provide a systematically analysis of changes in homocysteine levels following weight loss surgery.

Changes in homocysteine levels following bariatric surgery remain controversially discussed. Where some authors found postoperatively lower values (5, 6), others reported elevated values (7-10). Even some found no difference at all between preoperative and postoperative values of homocysteine (11-13). Some of these studies used outdated bariatric surgery procedures (7, 9, 13).

In literature the postoperative changes of homocysteine after bariatric surgery remain unrevealed. Therefore, we designed this survey to assess timeline changes of homocysteine with a long-time and high follow-up. This could be of importance to postoperative prophylaxis of cardiovascular disease events.

For homocysteine being only a surrogate parameter for cardiovascular events, we decided to reveal changes in homocysteine being of clinical relevance via assessing the actual cardiovascular disease events (stroke, myocardial infarction, deep veinous thrombosis, ...).

2 Outcome

The primary outcome is to assess timeline changes of the peri and postoperative values of homocysteine in $\mu\text{mol/l}$ via the CMIA (chemiluminescent microparticle immunoassay) through study completion. Secondary outcomes include

demographic parameters like weight, height, folate, and vitamin B12. Furthermore, for determining clinical relevance we assessed the postoperative newly-onset number of cardiovascular events.

3 Patients

All patients received laparoscopic roux-en-Y gastric bypass at the department of surgery at the medical university of vienna over a six year period. All patients met the criteria for bariatric surgery: BMI of above 40 kg/m^2 without comorbidities or BMI of above 35 kg/m^2 with comorbidities including diabetes mellitus, arterial hypertension, hyperlipidaemia, obstructive sleep apnea syndrome, arthrosis and others. Minimal age was 18 years and highest age was 75 years for inclusion. Both female and male participants were eligible.

4 Parameters

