4.2 Secondary outcomes

Secondary outcome measurements include folate, vitamin B12 being well known to have impact on homocysteine metabolism. Furthermore, all standard laboratory parameters and demographic data will be assessed also. The postoperative incidence of newly-onset cardiovascular disease events will be reported.

5 Methods

Retrospective analysis of existing records of the department of surgery, medical university of vienna will be performed. To extract laboratory values out of the database the Archimed software will be utilized.

To reveal clinical relevance of changes in homocysteine values we will perform postal screening utilizing a questionnaire in all 708 participants. In the same step the informed consent form will be sent to each patient and they will be questioned if they have experienced any cardiovascular disease event after surgery (see IC form and questionnaire). An encrypted form of these lists is only available to the principal investigator and the study nurses.

Finally, the data will be compared to two state wide databases (AKIM and Webokra) to verify cardiovascular events.

6 Statistics

Descriptives

Case number strategy: the number of participants include all patients undergoing roux-en-Y gastric bypass consecutively over a six year period. We expect 708 cases. For this study being only exploratory we forwent a formal Power analysis.

To reveal statistical relevant postoperative changes of homocysteine we performed paired t-tests between preoperatively. Pearson's or Spearman's Correlations will be performed to reveal the influence of folate and vitamin B12 on the homocysteine metabolism.

The results of the postal screening section will be evaluated descriptively and compared to general incidences of cardiovascular disease events.

7 Data privacy protection

All patients will be numbered continuously and anonymized for further evaluation. Only authorized personnel will be able to access original names and data.

Furthermore, data will be stored and evaluated on personal computers at the medical university of Vienna with restricted access.

8 Risk-benefit analysis

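### No perioperative period is set apart in the event count, so thrombosis provoked by the operation can inflate the venous part of the comparison with general incidences

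*Combined protocol and SAP*

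**What the plan says.** Section 1 (Background) names the events twice. The risk paragraph lists "cardiovascular events (myocardial infarction, stroke, acute limb ischemia, deep veinous thrombosis". The closing paragraph gives the events by which clinical relevance will be judged as "the actual cardiovascular disease events (stroke, myocardial infarction, deep veinous thrombosis", and the list is left open. Venous thrombosis is in both lists.

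Section 2 states the purpose: "for determining clinical relevance we assessed the postoperative newly-onset number of cardiovascular events". Section 4.2 gives the outcome: "The postoperative incidence of newly-onset cardiovascular disease events will be reported". Section 5 sets the window through a postal questionnaire in which "they will be questioned if they have experienced any cardiovascular disease event after surgery", and two databases are then used to verify events. Section 6 gives the analysis: "The results of the postal screening section will be evaluated descriptively and compared to general incidences of cardiovascular disease events".

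Section 4.1 schedules homocysteine before surgery and then from 3 to 96 months, so the first postoperative value is at 3 months. The text defines no perioperative period for events, no start of person-time, no rule on reporting by event type, and no source for the comparator rates.

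**The concern.** Every patient had an abdominal operation at the start of the observation window. A general incidence carries no such exposure. A venous thrombosis provoked by the operation therefore adds to the observed count and has nothing opposite it in the expected count.

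Such an event also says little about the study question. In the first weeks it occurs before any postoperative homocysteine value has been taken, so it cannot be related to a measured change. The window as worded still admits it as evidence on whether those changes matter.

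The expected number of venous events in a cohort of this size is small, so a handful of early thromboses could look like an excess when homocysteine has no effect. If venous and arterial events are also added together, opposite results in the two groups could be hidden. This comparison is the only analysis in the plan that addresses clinical relevance. The primary homocysteine outcome is not touched.

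**Working it through.** The plan states no event rate, follow-up time or expected count, so there is no figure of its own to reproduce. What follows is an illustration.

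**Input from the documents:** N = 708 (section 6: "We expect 708 cases").

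**Assumed inputs:** perioperative thrombosis risk p, background rate b, person-years PY, and the share s of events that the questionnaire captures. The true ratio outside the perioperative period is set to 1.

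**Formulas:** extra events x = N × p; expected events E = b × PY; observed/expected ratio = (E + x)/E. If a share s of all events is captured, the ratio is s(E + x)/E, and it equals 1 at s = E/(E + x).

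**1. Extra events**
- p = 0.3%: 708 × 0.003 = 2.1
- p = 1%: 708 × 0.01 = 7.1
- p = 2%: 708 × 0.02 = 14.2

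**2. Thrombosis alone** (b = 1 to 3 per 1000 PY; PY = 2100 to 5000)
- Smallest effect: E = 0.003 × 5000 = 15; ratio (15 + 2.12)/15 = 1.14
- Mid case: E = 0.0015 × 3500 = 5.25; ratio (5.25 + 7.08)/5.25 = 2.35
- Largest effect: E = 0.001 × 2100 = 2.1; ratio (2.1 + 14.16)/2.1 = 7.74

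**3. Composite of arterial and venous events**
- Mid case A: p = 0.5%, b = 5 per 1000, mean follow-up 4 years. PY = 708 × 4 = 2832; E = 14.16; x = 3.54; ratio 17.70/14.16 = 1.25
- Mid case B: p = 1%, b = 5 per 1000, PY = 3500. E = 17.5; x = 7.08; ratio 24.58/17.5 = 1.40
- Over p = 0.2% to 2%, b = 3 to 10 per 1000 and follow-up of 2 to 8 years, the ratio runs from 1.02 to 4.33.

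The composite ratio is smaller in the mid cases because infarction and stroke enlarge the expected count while the extra events stay the same.

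**4. Incomplete capture** (composite mid case A)
- s = 0.80: 0.80 × 1.25 = 1.00
- s = 0.70: 0.70 × 1.25 = 0.875
- Over the grid in step 3, the break-even share runs from 4.25/(4.25 + 14.16) = 0.23 to 56.64/(56.64 + 1.42) = 0.98.

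The venous component is pushed upward, but the overall ratio can fall on either side of 1.

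**5. What a 90-day landmark removes:** 708 × 90/365.25 = 174 person-years, which is 8.3% of 2100, 5.0% of 3500 or 3.5% of 5000. At 1 to 3 per 1000 PY that is 0.2 to 0.5 expected thromboses. With full capture, the ratio in steps 2 and 3 returns to 1.00.

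**The case against.** A reader might infer that the plan counts from the day of surgery, pools all event types into one rate, and so yields a result that is biased upward. The documents do not go that far.

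- **Start of counting.** The text says only that events follow surgery. An early start is the plain reading of a window with no exclusion, but it is not a stated rule.
- **Pooling.** Section 6 speaks of incidences in the plural, which fits a comparison type by type. Separate reporting would keep the problem out of the arterial results, though the venous line would still carry it.
- **Net direction.** The questionnaire goes out with the consent form, and the databases are described only as verifying events. Non-response, missed deaths and poor recall all lower the count. Comparator rates without stated standardisation for age, sex or obesity could push either way. An upward net bias is therefore not established.
- **Instrument.** The questionnaire is not in the public text. It may already record event type and date.
- **Weight.** The comparison is secondary and descriptive, in a study that calls itself exploratory. It is not a test and has no decision rule.

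All of this stands, and it limits the claim to the venous component. It does not remove the point. Under-capture is a separate error of unknown size; that it might offset the perioperative excess is no reason to leave both in. Once early events are set apart, any under-capture would show more clearly.

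**Conclusion.** The point holds for the venous part of the comparison. As worded, the window admits operation-provoked thrombosis, the comparator has no counterpart, and early events cannot bear on a homocysteine change first measured at 3 months. This can inflate the thrombosis comparison, by a factor of about 1.1 to 7.7 on the assumed rates. A composite would move less, by about 1.25 to 1.4 in mid cases. These ratios assume complete capture and no true effect, and every rate and follow-up figure is an assumption.

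The net direction of the whole event comparison is not determined. The matter should be settled before the event results are interpreted; it does not affect the primary outcome.

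**What to change.** In sections 4.2 and 6:

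1. Report arterial events (infarction, stroke, limb ischaemia) and venous thrombosis separately, each against a rate for the same event type from a named source.
2. Fix an analysis landmark, for example 90 days after surgery, which is close to the first postoperative homocysteine value. Report events of every type before it separately, as perioperative.
3. Start both events and person-time for the population comparison at that landmark.
4. Take event dates from the questionnaire or from AKIM/Webokra where available, and state how events without a date are handled.

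The cost is a change of wording and one date per event, with no new patients or assays. The documents do not show whether these sources hold dates, so dates may have to be requested. The comparison loses a few events and, on the assumed follow-up, about 3.5% to 8.3% of its person-time.

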4.1 Primary outcome

Homocysteine in $\mu\text{mol/l}$ assessed by CMIA technique at the timepoints preoperatively, 3, 6, 9, 12, 18, 24, 36, 48, 60, 72, 84 and 96 months postoperatively. Timeframe: through study completion.

4.2 Secondary outcomes

Secondary outcome measurements include folate, vitamin B12 being well known to have impact on homocysteine metabolism. Furthermore, all standard laboratory parameters and demographic data will be assessed also. The postoperative incidence of newly-onset cardiovascular disease events will be reported.

5 Methods

Retrospective analysis of existing records of the department of surgery, medical university of vienna will be performed. To extract laboratory values out of the database the Archimed software will be utilized.

To reveal clinical relevance of changes in homocysteine values we will perform postal screening utilizing a questionnaire in all 708 participants. In the same step the informed consent form will be sent to each patient and they will be questioned if they have experienced any cardiovascular disease event after surgery (see IC form and questionnaire). An encrypted form of these lists is only available to the principal investigator and the study nurses.

Finally, the data will be compared to two state wide databases (AKIM and Webokra) to verify cardiovascular events.

6 Statistics

Descriptives

Case number strategy: the number of participants include all patients undergoing roux-en-Y gastric bypass consecutively over a six year period. We expect 708 cases. For this study being only exploratory we forwent a formal Power analysis.

To reveal statistical relevant postoperative changes of homocysteine we performed paired t-tests between preoperatively. Pearson's or Spearman's Correlations will be performed to reveal the influence of folate and vitamin B12 on the homocysteine metabolism.

The results of the postal screening section will be evaluated descriptively and compared to general incidences of cardiovascular disease events.

7 Data privacy protection

All patients will be numbered continuously and anonymized for further evaluation. Only authorized personnel will be able to access original names and data.

Furthermore, data will be stored and evaluated on personal computers at the medical university of Vienna with restricted access.

8 Risk-benefit analysis

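### Cardiovascular events are collected to show whether homocysteine changes matter clinically, but no planned analysis relates the two, and the comparison with general incidences cannot do so

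*Combined protocol and SAP*

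**What the plan says.** **Why events are collected.** Section 1 (Background) treats homocysteine as a surrogate and continues: "we decided to reveal changes in homocysteine being of clinical relevance via assessing the actual cardiovascular disease events". Section 5 (Methods) repeats the purpose for the survey: "To reveal clinical relevance of changes in homocysteine values we will perform postal screening utilizing a questionnaire in all 708 participants". Section 2 (Outcome) is weaker. It says "for determining clinical relevance we assessed the postoperative newly-onset number of cardiovascular events", and that sentence does not mention homocysteine changes.

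**How events are defined and obtained.** Section 4.2 promises incidence only: "The postoperative incidence of newly-onset cardiovascular disease events will be reported". Under section 5 patients are asked by post: "they will be questioned if they have experienced any cardiovascular disease event after surgery". The answers are then checked: "Finally, the data will be compared to two state wide databases (AKIM and Webokra) to verify cardiovascular events".

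**What is analysed.** Section 6 names three analyses:

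1. paired t-tests for postoperative change in homocysteine;
2. Pearson or Spearman correlations of folate and vitamin B12 with homocysteine;
3. a description of the survey results and a comparison with general incidences of cardiovascular events.

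Section 6 also calls the study exploratory and waives a power analysis. Section 8 presents the results as a basis for further hypotheses.

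**The concern.** The survey exists, by its own rationale, to answer a question about homocysteine changes. The only analysis planned for the survey data leaves homocysteine out. If section 6 is followed exactly, the report will place a homocysteine time course beside a cohort event rate. A reader could take a high rate as evidence that the changes matter, or a low rate as evidence that they do not. Neither conclusion would follow.

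What is at stake is this one stated question. All 708 patients are to be contacted about their health partly in order to answer it.

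**Working it through.** **Step 1: variables in each planned analysis.**

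| Section 6 analysis | Homocysteine | Events |
|---|---|---|
| Paired t-tests | yes | no |
| Correlations with folate and vitamin B12 | yes | no |
| Survey description, compared with general incidences | no | yes |

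Analyses with both: 0 of 3. The database step in section 5 verifies events and is not an association analysis. Section 4.2 adds only the reporting of incidence. No other section plans an analysis of the two together.

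**Step 2: can the incidence comparison stand in for it?** Split the cohort into equal halves, with larger and smaller homocysteine change. Let T be the total number of events and R the ratio of event risk between the halves. Then:

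- events in the upper half = T × R / (1 + R)
- events in the lower half = T / (1 + R)
- sum = T × (R + 1) / (1 + R) = T, for every R.

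The comparison with general incidences uses T, the follow-up time and the reference rates. R does not enter it.

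**Step 3: illustration.** The cohort size of 708 comes from section 6. The documents give no event rate, so I assume that 2%, 5% or 10% of patients have an event and that all 708 have event information. T is then 708 × 0.02 = 14.16, 708 × 0.05 = 35.4 or 708 × 0.10 = 70.8.

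| T (assumed) | R = 1 | R = 2 | R = 3 |
|---|---|---|---|
| 14.16 | 7.08 and 7.08 | 9.44 and 4.72 | 10.62 and 3.54 |
| 35.4 | 17.7 and 17.7 | 23.6 and 11.8 | 26.55 and 8.85 |
| 70.8 | 35.4 and 35.4 | 47.2 and 23.6 | 53.1 and 17.7 |

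Each row has one total, so the external comparison gives the same answer under no association and under a threefold one. A lower response would reduce T but leave the algebra unchanged.

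**Step 4: the reverse direction.** Suppose the cohort rate differs from the general rate. Section 3 admits patients with "BMI of above 40 kg/m^2 without comorbidities or BMI of above 35 kg/m^2 with comorbidities", and all of them had the operation. Either the selection or the surgery could produce the difference with R = 1. An unusual rate is therefore not evidence for a role of homocysteine, and an ordinary rate is not evidence against one.

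**The case against.** The strongest reply is that the plan asks a cohort-level question: homocysteine changes after surgery, so is event incidence in these patients unusual? Section 6 does address that. The study is exploratory, the text is a translation, and section 4.2 promises incidence and nothing more. On this reading there is little to repair beyond wording.

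Part of this stands. The incidence outcome is defined and analysed, and the exploratory label justifies the absence of a powered test. The cohort-level reading does not rescue the stated purpose, though. Sections 1 and 5 refer to the relevance of homocysteine changes, and steps 2 to 4 show that the cohort rate does not bear on that. The exploratory label does not supply a missing analysis. Section 6 already plans associations of homocysteine with folate and vitamin B12, so an association analysis would fit the design.

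A second reply is that a descriptive evaluation could include a table by homocysteine. It could; a reader might infer that the plan rules this out, and it does not. But no table is specified, so the visit, grouping and timing would be open to choice after the data are seen.

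A third reply is that an unadjusted comparison cannot establish clinical relevance either. That is correct. Folate, vitamin B12 and comorbidities could explain a difference. Such a comparison shows association only, but unlike the planned one it does contain both variables.

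**Conclusion.** The mismatch is real and limited. Two sections tie the collection of events to homocysteine changes, none of the three planned analyses relates them, and the external comparison is the same whatever the association within the cohort. The count and the algebra rest on no assumed rate; only the table in step 3 does.

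Three stronger readings are not supported:

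- **That the main results are compromised.** The primary outcome (homocysteine over time) and the reporting of event incidence are unaffected.
- **That the aim is stated three times in the same terms.** Section 2 refers to clinical relevance without naming homocysteine changes.
- **That the precision of a homocysteine-by-event comparison can be forecast.** The documents give neither an event rate nor a response rate, so no interval width is offered here.

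The change is worth making, because the comparison as planned invites a conclusion that it cannot support. It is not a reason to doubt the rest of this exploratory study.

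**What to change.** In section 6:

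1. State that the comparison with general incidences describes event incidence after surgery and is not evidence for or against the clinical relevance of homocysteine changes.
2. Add one exploratory patient-level comparison among patients with event information. Take the homocysteine change from the preoperative value to one postoperative visit, fixed in advance from the 12 in section 4.1 (the last three being "72, 84 and 96 months postoperatively"). Compare patients with an event after that visit with patients who had none. Give the difference and 95% CI, with the numbers of responders, events and patients with values, and label it an unadjusted association.
3. If event dates, or the link between survey and laboratory data, are not available, do not run item 2. Instead restate the aim in sections 1, 2 and 5 as describing event incidence after surgery.

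**Cost.** Item 1 is one sentence and item 2 one short table; item 3 is rewording and needs no data. Two things must be confirmed before item 2:

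- **Dates.** Section 5 says patients are asked whether an event occurred. The questionnaire is not in the text reviewed, and the text does not say whether the two databases hold dates. The tenses in sections 2 and 5 differ, so the survey may already be done; in that case any missing dates would have to come from the databases.
- **Linkage.** Section 7 numbers patients and lets authorised staff reach the original data, so linkage looks feasible, but the same section speaks of anonymisation.

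**Downsides of item 2.** Few events and wide intervals are likely, and events before the chosen visit are lost. Confounding remains, for example by folate, vitamin B12 and comorbidities. Responders may differ from non-responders, and patients who died cannot answer the questionnaire.

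### The folate and B12 correlation has no stated visit, scale or unit of analysis, although each patient has up to 13 scheduled samples

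*Combined protocol and SAP*

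**What the plan says.** Section 2 Outcome sets the target: "The primary outcome is to assess timeline changes of the peri and postoperative values of homocysteine". Section 4.1 schedules homocysteine "preoperatively, 3, 6, 9, 12, 18, 24, 36, 48, 60, 72, 84 and 96 months postoperatively", which is 1 preoperative and 12 postoperative timepoints, 13 in all. Section 4.2 lists the vitamins as secondary: "Secondary outcome measurements include folate, vitamin B12 being well known to have impact on homocysteine metabolism". It gives them no sampling times of their own.

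Section 6 Statistics gives one sentence to each analysis. For homocysteine: "To reveal statistical relevant postoperative changes of homocysteine we performed paired t-tests between preoperatively". The sentence is incomplete, but a paired test is a within-patient comparison. For the vitamins: "Pearson's or Spearman's Correlations will be performed to reveal the influence of folate and vitamin B12 on the homocysteine metabolism". No visit, scale, unit of analysis or treatment of repeated samples is given, and no model is named. On numbers, the section says "We expect 708 cases" and "For this study being only exploratory we forwent a formal Power analysis".

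**The concern.** The standard p-value of a Pearson or Spearman correlation assumes independent pairs, one pair per subject. Here a patient may contribute up to 13 pairs. An extract from a laboratory database may well hold one row per sample, so a pooled analysis is a realistic way to carry out the sentence, and nothing in the plan rules it out.

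The sentence allows three readings:

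- **All samples pooled.** Repeated samples from one patient count as separate patients, and p-values are too small.
- **Values at one visit.** The pairs are independent, but different people are compared. Lasting differences between people enter the coefficient along with the effect of a change in vitamin level.
- **Changes from the preoperative value.** This asks whether the patients whose folate or B12 fell are those whose homocysteine rose, which is the question closest to the primary outcome.

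The readings can give different answers from the same data, and the plan does not choose between them. Section 8 offers the results as a basis for new hypotheses, so a spurious or masked vitamin link would carry over into later work.

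**Working it through.** The plan gives no alpha, SD, intraclass correlation (ICC) or expected correlation for this analysis, so there is no figure of its own to reproduce. From the documents: 13 scheduled timepoints and 708 expected patients. Assumed: two-sided alpha 0.05, the ICCs, the true correlations and the number of samples per patient. The calculations use Pearson correlation on normal data.

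**1. Samples pooled, no true association.** With m samples per patient, the variance of the correlation is inflated by about D = 1 + (m − 1) × ICC(homocysteine) × ICC(vitamin). The actual test size is 2 × [1 − Φ(1.96/√D)]. With ICCs of 0.6 and 0.5 the product is 0.30.

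| m | D | 1.96/√D | Actual size of a 5% test |
|---|---|---|---|
| 4 | 1 + 3 × 0.30 = 1.9 | 1.42 | 15.5% |
| 6 | 1 + 5 × 0.30 = 2.5 | 1.24 | 21.5% |
| 13 | 1 + 12 × 0.30 = 4.6 | 0.91 | 36% |

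Simulations agree: 14% to 17% at 4 samples, 22% to 24% at 6 and 36% to 37% at 13. Sensitivity at 13 samples, with both ICCs equal to 0.3, 0.5 or 0.7: D = 2.08, 4.00 and 6.88, and sizes of 17%, 33% and 46%. At 5 samples: 9%, 17% and 26%. Adding unrelated, opposite time trends of 0.5 SD in total (13 samples, both ICCs 0.5) raised the simulated size from 32% to 58%.

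**2. Values at one visit.** The simulated size under the null was 4% to 6%, so this reading is not falsely significant. The difficulty is what it estimates. With equal ICCs:

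value correlation = ICC × r(between) + (1 − ICC) × r(within).

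| r(within) | r(between) | ICC 0.3 | ICC 0.5 | ICC 0.7 | Against r(within) |
|---|---|---|---|---|---|
| −0.30 | 0 | −0.21 | −0.15 | −0.09 | diluted |
| −0.30 | −0.30 | −0.30 | −0.30 | −0.30 | equal |
| −0.30 | +0.30 | −0.12 | 0 | +0.12 | diluted, hidden or reversed |
| 0 | −0.30 | −0.09 | −0.15 | −0.21 | overstated |

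**3. Changes from preoperative.** The patient's lasting level cancels in the subtraction. A trend common to all patients drops out because the correlation is taken within one visit. Simulated size was about 5% (0.049 to 0.059 in the settings without a trend). With a true within-patient correlation of −0.30, the estimate was about −0.30 whatever the between-patient value.

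**4. Does an all-visit version need a time term?** Suppose there is no patient-level link, but homocysteine and the vitamin follow opposite linear trends whose SD across visits is 0.2 within-patient SD (assumed, 300 patients). A within-patient correlation without a visit term then has expected size s/(1 + s), with s = 0.04 × m/(m − 1). At m = 4, s = 0.0533 and r = 0.051 in magnitude. The test statistic is about 0.051 × √(300 × 3) = 1.52, and rejection is about 33%. At m = 13, s = 0.0433 and r = 0.042. The statistic is about 0.0415 × √(300 × 12) = 2.49, and rejection is about 70%. Simulation gave 34% to 72%, against about 5% to 6% with visit included. The time term is therefore necessary.

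**The case against.** The strongest reply is that the plan commits no error here. It does not say that values are correlated, nor that samples are pooled. Pearson and Spearman apply equally to change scores, and the sentence just before concerns postoperative change. This stands: the defect is missing specification, not a wrong choice.

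A reader might infer that the planned correlation must understate the vitamin effect. The documents do not support that. Dilution needs a between-patient correlation weaker than the within-patient one, and the plan gives neither. With −0.50 for both there is no dilution. With −0.70 between and −0.50 within, the value correlation is 0.3 × (−0.70) + 0.7 × (−0.50) = −0.56 at ICC 0.3 and −0.64 at ICC 0.7, which is overstated.

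A reader might also infer that the stated purpose is to find what drives the postoperative change. The plan speaks of influence on homocysteine metabolism, and a same-visit correlation of values is a fair descriptive answer to that. The within-patient question is an inference from the primary outcome.

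Finally, this is a secondary analysis, the study is exploratory, no alpha is declared, and records may hold fewer than 13 samples per patient. All of that lowers the priority. It does not make repeated samples independent: the exploratory label is used to explain the absence of a power calculation, and the inflation is already about 15% at 4 samples under the assumed ICCs.

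**Conclusion.** The point holds as one of under-specification. Section 6 leaves open an invalid reading (pooling, with about 15% to 37% false positives at a nominal 5% for 4 to 13 samples per patient) and a valid but ambiguous one (values at one visit, correct size, no fixed relation to the within-patient link). It does not name the reading that matches the primary outcome. The percentages rest on assumed ICCs of 0.5 and 0.6 and on every patient having the same number of samples. They shrink towards 5% if either ICC is near zero or samples are few, and grow with common time trends. Severity is low to moderate.

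**What to change.** Replace the correlation sentence in section 6 with:

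- **(a) Per visit.** At each postoperative visit, Spearman correlation of the change from preoperative in homocysteine with the change from preoperative in folate, and separately in B12, using values from the same blood draw. With 12 visits and two vitamins this is 24 coefficients, so report them as exploratory.
- **(b) Across visits.** A mixed model for homocysteine with a patient random intercept, visit as a categorical factor, and folate and B12 each entered as the patient's mean and the deviation from it. A within-patient correlation adjusted for visit is an acceptable alternative. The visit factor guards against shared trends. The split is needed because a plain random intercept still mixes the between-patient and within-patient associations.
- **(c)** State that samples will not be pooled as independent, and that single-visit correlations of values are descriptive.

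The cost is plan wording and a few lines of code, with no new data collection. Patients without a preoperative vitamin value drop out of (a) but stay in (b).
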